### *Variables and Procedures*

Within 24-48 hours from symptoms, onset full panel of stool cultures will be performed together with Clostridium toxin assessment. Multiparametric ultrasound study will be performed at the onset of the symptoms and then weekly to monitoring intestinal changes accordingly to symptoms evolution during treatment. In the case with high suspicion for aGvHD (stool culture negative, persistent or progressive diarrhea, ultrasound imaging closely suggestive for aGvHD), as per common clinical practice, colonoscopy will be required to evaluate internal macroscopy features of the bowel and to obtain histological samples for conclusive diagnosis. In the meantime steroid therapy will be started, as per common clinical practice. The only modification of this protocol to common clinical practice is represented by the addition of a non-invasive bed-side method of evaluation of the patients with diarrhea. None of the routinely performed diagnostic and therapeutic process will be modified.

All patients submitted to autologous stem cell transplant who developed diarrhea between transplant date and engraftment achievement will constitute control population. Also in this case full panel of stool culture and clostridium toxin assessment will be performed at the onset of the symptoms. Multiparametric ultrasound study will be made at symptoms onset and then weekly until symptom resolution.

Multiparametric ultrasound study will be performed by expert qualified staff as following:

The examinations will be performed at patient's bed, in supine position, with a MyLab™9 Platform (Esaote, Italy) system. Fasting is required.

US for bowel requires both low-frequency convex probes (3.3-5 MHz) and high-frequency (5–17 MHz) linear assay probes to increase the spatial resolution of the intestinal wall and to assess the wall diameter and wall layer.

The following ultrasound parameters will be collected:

- Intestinal wall thickening (normal values < 3 mm; a mean of two measurements for section will be taken, in longitudinal and transverse sections).
- Intestinal wall stratification;
- Intestinal wall flow at colorDoppler;
- Strictures;
- Free fluid (FF) within the peritoneal cavity;
- Enlarged mesenteric lymph nodes;
- Mesenteric hypertrophy.

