The contrast agent is administered intravenously and excreted through the lungs without risk of nephrotoxicity or ionizing radiation as in the case of computed tomography contrast agent; it does not remain in the body longer than 15 min. It consists of microscopic bubbles of gas (size 3–5  $\mu\text{m}$ ), which are encapsulated in a shell of flexible and stiff phospholipids: they enhance the backscatter signal from blood cells, oscillating when exposed to a low-intensity US field, thereby demonstrating tissue perfusion in real-time “blood-pool”

imaging. SonoVue (SV, Bracco, Italy) is actually the second-generation US contrast agent used for CEUS, consisting of phospholipid-stabilized microbubbles filled with sulphur hexafluoride. The recommended dose of SonoVue is 2.4 mL. Every injection should be followed by a flush with 5-10 mL of 9 mg/mL (0.9%) sodium chloride solution. Approximately, 10–15 s after intravenous injection, the SonoVue arrives to the intestinal wall, thereby achieving the maximum concentration (peak intensity) after approximately 30 s. This stage is followed by a venous phase, and it is finally excreted by the lungs. No adverse event was reported with SonoVue use: the only contraindication is severe cardiomyopathy (7-9).

The following CEUS parameters will be collected:

- Time-intensity curve (TIC) included basic intensity (B), wash-out slope and/or decent slope (K), wash-in slope or rise slope (C), time to peak (TTP), area under the gamma curve (Area), arrive time (ATM), peak intensity (PI), change of peak intensity (I).
- Any exam will be recorded;
- Acquisition time: 5'

Moreover, each single evaluation will be completed with the use of SWE in order to further evaluate the characteristics of the inflammatory bowel.

SWE of the bowel wall will be performed according to manufacturer guidelines

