### *Statistical Analysis*

All variables included in the study will be first analyzed by descriptive statistic techniques. In depth, qualitative variables will be described as absolute and relative percentage frequencies. The Shapiro Wilk's test will be used to assess the distribution of quantitative variables. Data will be then expressed either as mean and standard deviation (SD), whether normally distributed, or as median and interquartile range (IQR), otherwise.

Between groups differences (allogenic vs. autologous transplant) will be assessed by the Fisher exact test and the Chi-square test, with Yates correction, as appropriate, in the case of qualitative variables. Quantitative data, indeed, will be assessed either by the Student's t test or the non-parametric Mann Whitney U test, as appropriate.

Receiver Operating Curve (ROC) analysis will be used to assess the accuracy of multiparametric bedside ultrasound in aGvHD diagnosis as compared to the histologic diagnosis (gold-standard, used as reference). Positive (PPV) and Negative predictive values (NPV), sensitivity and specificity will be computed, as well as the area under the ROC curve (AUROC).

To assess potential associations between bed-side multiparametric ultrasound measurements and aGvHD diagnosis in patients underwent to allogenic transplant uni- and multivariable logistic regression models will be used.

Logistic regression models will be also applied to assess whether bed-side multiparametric ultrasound (US) measurements differ in distinguishing complications different from aGvHD (i.e., infectious, drug-related or neutropenic colitis) in patients underwent to allogenic transplant as compared to auto-transplant. More in depth, to evaluate the combined effects between US measurements and transplant group, multivariable interaction models will be fitted, and the interaction odd ratios (IOR) evaluated. In particular, for each US measurement, one interaction logistic regression model will be fitted. In summary, the coefficients of the main effects (in exponential terms) will be interpreted as ORs of the outcome by considering the allo-transplant group from control ( $OR_{\text{autologous}}$ ), by

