fixing US measurements values to 0 (null), and ORs of the outcome by considering a unit increase of the US measurements in the auto-transplant group ( $OR_{US\_measurements}$ ). The interaction parameters (IOR) will be interpreted as difference (in OR terms) of the US measurements variations between transplant groups (autologous transplant as reference category).

Statistical significance will be set at P value  $< 0.05$ . P values between 0.05 and 0.10 will be further reported as suggestive. All analyses will be performed by using R software (v. 4.1.2, R Core Team, 2021) [11].

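### The interaction models read the allogeneic/autologous OR at an ultrasound value of 0, which cannot occur for wall thickness or time to peak; centring would make this secondary OR interpretable at no cost

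*Combined protocol and SAP*

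**What the plan says.** Under Statistical Analysis, the SAP addresses the second secondary endpoint with logistic models: "for each US measurement, one interaction logistic regression model will be fitted". Three quantities are to be interpreted from each model.

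- **Group main effect.** Its exponential is among the coefficients that "will be interpreted as ORs of the outcome by considering the allo-transplant group from control", and it is read by "fixing US measurements values to 0 (null").
- **Ultrasound main effect.** This is the OR per unit increase in the autologous group.
- **Interaction OR (IOR).** This is the difference between groups in the ultrasound effect, with autologous transplant as reference.

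No centring, scaling or other reference value is mentioned. A general threshold follows ("Statistical significance will be set at P value" below 0.05), with values from 0.05 to 0.10 to be reported as suggestive.

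Under Variables and Procedures, the measurements include "Intestinal wall thickening (normal values < 3 mm") and "time to peak (TTP"). That section has contrast reaching the bowel wall about 10 to 15 s after injection, "thereby achieving the maximum concentration (peak intensity) after approximately 30 s".

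**The concern.** In a model with an interaction, the group coefficient is the group effect at the single point where the other variable is 0. For free fluid, strictures or enlarged nodes, 0 means absent and is a sensible reference. For wall thickness in millimetres or time to peak in seconds, no patient can have the value 0. The OR then describes a patient who cannot exist, and it is estimated by extending two fitted lines beyond the data.

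Two things follow for such measurements. The confidence interval is much wider than it would be at a typical value. If the ultrasound effect differs between groups, the OR at 0 is also a different number from the OR at any observed measurement. At stake is one of the three quantities that the SAP says it will interpret from every interaction model.

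**Working it through.** The documents give no figure for this OR, so there is nothing to reproduce. The check is algebra followed by simulation.

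**Inputs from the documents.** 75 allogeneic patients and an equal number of autologous patients (Sample Size calculation); contrast arrival at 10 to 15 s and peak at about 30 s after injection (Variables and Procedures); significance level 0.05.

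**Assumed, because the documents give none.** Means and SDs of wall thickness, SDs of time to peak, outcome risk, ultrasound slopes and the size of any interaction. The outcome is taken to vary in both groups.

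**Step 1: what centring changes.** With G = 1 for allogeneic, logit p = b0 + b1·G + b2·US + b3·G·US. Replacing US by US − c turns the group coefficient into b1 + b3·c. The values of b2, b3, their standard errors and the log-likelihood do not change. In simulated fits the raw and centred versions of these agreed to rounding error.

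**Step 2: loss of precision at 0.** With similar distributions in two equal groups, the group effect at the mean and b3 are nearly uncorrelated, and Var(b3) is about Var(group effect at the mean)/SD². Hence Var(group effect at 0) ≈ Var(at the mean) × [1 + (mean/SD)²], and the standard error (SE) ratio is sqrt(1 + (mean/SD)²).

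| Measurement | Mean | Assumed SD | SE ratio |
|---|---|---|---|
| Wall thickness | 4.5 mm (assumed) | 1.5 mm | sqrt(1+9) = 3.2 |
| Wall thickness, range | 3.5 to 5.5 mm (assumed) | 1.0 to 2.0 mm | 2.0 (3.5/2.0) to 5.6 (5.5/1.0) |
| Time to peak, from injection | about 30 s | 5 to 15 s | 6.1 (30/5) to 2.2 (30/15) |
| Time to peak, from arrival | 30 − 15 = 15 s to 30 − 10 = 20 s | 5 to 15 s | 4.1 (20/5) to 1.4 (15/15) |

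Both time origins are shown because the protocol lists arrival time as a separate parameter and does not say where time to peak starts.

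**Step 3: simulation at 75 + 75.** Settings: 2000 runs, outcome risk 30%, wall thickness 4.5/1.5 mm truncated below 1 mm, no group effect. The median SE of the group log-OR was 1.27 at 0 and 0.37 at the mean. The 95% interval is therefore the OR multiplied or divided by exp(1.96 × 1.272) = 12.1 at 0, and by exp(1.96 × 0.367) = 2.1 at the mean. The simulated ratio (about 3.5) is a little above the formula, partly because truncation narrows the spread.

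**Step 4: shift in value, only if there is an interaction.** Take a group OR of 1.0 at 4.5 mm and an assumed IOR of 1.25 per mm. At 0 the OR is 1.25^(−4.5) = 0.37. With a simulated SE of 1.335, the 95% interval is 0.366 × exp(±1.96 × 1.335), or 0.03 to 5.0.

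**Step 5: when centring cannot help.** With the outcome set constant in the autologous group, the group log-OR was near −24 with an SE above 10,000, both raw and centred.

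**The case against.** The strongest case on the other side is that little is lost. The secondary endpoint asks whether the measurements distinguish complications differently in the two transplant groups. The IOR answers that, and centring does not change it. The SAP is open that the group OR is conditional on 0, which is a correct reading of an uncentred model. The OR at any other value c, exp(b1 + b3·c), can be recovered from the same fit. All of this stands. What remains is that the plan names 0 as the value to report, and that a reference value chosen after seeing the results would be post hoc.

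A reader might infer that the trial loses power to detect a group difference. For a true OR of 3 in the wall-thickness scenario, the coefficient at 0 reaches P < 0.05 in about 15% of runs, against 91% at the mean. The documents do not support that inference. Statistical Analysis also plans direct allogeneic/autologous comparisons of qualitative variables by Fisher or Yates-corrected chi-square test, and a binary complication outcome is such a variable. In the same scenario those tests have about 88% power. For a true OR of 2 the Yates test has 45%, against 53% for the centred coefficient.

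A reader might also take 30 s as the protocol's mean for time to peak. It is the time of peak after injection, and time to peak counted from arrival would be shorter.

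The benefit is also conditional. Statistical Analysis does not state what counts as event and non-event in these models. The text points away from aGvHD, which has its own models in allogeneic patients, while Population makes autologous patients controls for other complications. If the outcome were nevertheless aGvHD against everything else, one would expect no variation in autologous patients, and centring would then cure nothing.

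**Conclusion.** The point holds as a minor, free improvement. For strictly positive continuous measurements, the planned allogeneic/autologous OR is an extrapolation to a value that cannot be observed. Under the stated assumptions its SE is about 3 times that at the mean for wall thickness, and between 1.4 and 6.1 times for time to peak, depending on its SD and time origin. The sizes depend on assumed distributions. The direction does not, and neither does the invariance of the IOR.

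Without an interaction, the usual result is an uninformative OR rather than a misleading one; with an interaction, its value shifts as well. The gain from centring is a secondary OR that can be interpreted and is more precise. It does not recover trial power or change the primary endpoint. All of this requires an outcome for which both event and non-event can occur in both transplant groups.

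**What to change.** In Statistical Analysis, replace the clause that fixes the measurement at 0 with:

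> Each continuous US measurement is centred at its overall mean (or overall median if non-normal) before the interaction term is formed; the allo/auto OR is reported at that value, which is stated; present/absent findings stay coded 0/1.

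This follows the SAP's own descriptive rule of mean and SD if normal, "or as median and interquartile range (IQR), otherwise".

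The cost is one sentence. It needs no new data or procedures, and the model fit and IOR stay the same. The centre depends on the sample, so its value must be reported with the OR. Using the median for a skewed measurement loses almost nothing. For an assumed log-normal time to peak with median 30 s, the SE was 0.353 at the median against 0.349 at the mean (log-SD 0.3), and 0.360 against 0.353 (log-SD 0.5).

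One further sentence should state the event and non-event coding of the outcome in these models, chosen by the sponsor so that both can occur in both transplant groups.

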### *Secondary endpoints*

- To assess potential associations between bed-side multiparametric ultrasound measurements weekly performed and aGvHD diagnosis in patients underwent to allogenic transplant.
- To assess whether bed-side multiparametric ultrasound measurements at baseline differ in distinguishing complications different from aGvHD (i.e., infectious, drug-related or neutropenic colitis) in patients underwent to allogenic transplant as compared to auto-transplant.

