## STATISTICAL ANALYSIS PLAN

### *Sample Size calculation*

The literature reports various experiences on the use of SWE in the study of the intestine, especially in patients with chronic inflammatory bowel diseases. But no data are reported on the use of the method in patients with graft versus host disease. Hence, we consider this as a pilot study. As such, no formal sample size calculation is needed. However, based on common rules on pilot studies [10], the minimum sample size required would be of 20 subjects. In our department, given the median annual number of allogenic stem cell transplant, we plan to enroll 75 patients. As for the secondary endpoints, an equal number of age-matched patients undergone to autologous transplant will be enrolled.

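### The interaction odds ratio tests per-unit effect modification, so secondary endpoint 2 also needs group-specific measures of discrimination (minor, cheap to add)

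*Combined protocol and SAP*

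**What the plan says.** The second item under Secondary endpoints reads in part: "To assess whether bed-side multiparametric ultrasound measurements at baseline differ in distinguishing complications different from aGvHD", with allogeneic patients compared with autologous ones. The Statistical Analysis section repeats the question and answers it by logistic regression: "for each US measurement, one interaction logistic regression model will be fitted". The measurement's main effect is read as "ORs of the outcome by considering a unit increase of the US measurements in the auto-transplant group", that is, per raw unit with no standardisation. The interaction term is then read as follows: "The interaction parameters (IOR) will be interpreted as difference (in OR terms) of the US measurements variations between transplant groups".

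ROC analysis, AUROC, sensitivity, specificity and predictive values are planned in the same section, but only for aGvHD diagnosis against histology. The allogeneic-versus-autologous t, Mann-Whitney, Fisher and chi-square tests compare levels of a variable between groups. They do not compare how well a measurement separates patients with and without a complication.

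On numbers, Sample Size calculation says "we plan to enroll 75 patients" for the allogeneic group and "an equal number of age-matched patients undergone to autologous transplant will be enrolled". The level is 0.05. No SD, AUROC, IOR or power is given for this endpoint.

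**The concern.** Whether a measurement distinguishes complications differently in two groups is, on its ordinary reading, a question about discrimination, with the null that discrimination is equal. The IOR has another null: that the OR per millimetre, per second or per intensity unit is equal. If the spread of a measurement differs between the transplant groups, the two can disagree in either direction. A significant IOR might be reported as a difference in diagnostic behaviour when only the spread differs, or a real difference in discrimination might be reported as absent.

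Unequal spread is possible here. Under Population, allogeneic patients enter with diarrhoea above 500 ml per day at any time up to day 100. Autologous patients enter only between transplant and engraftment, with no volume threshold stated.

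**Working it through.** **Nothing to reproduce.** The plan has no calculation for this endpoint. The 75 comes from annual transplant numbers, with an equal autologous group (150 in all).

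**Inputs from the documents.** 75 per group; level 0.05 (two-sided assumed); logistic slope per raw unit; IOR = allogeneic per-unit OR divided by autologous per-unit OR.

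**Assumed inputs.** Normal measurement with equal variance for outcome present and absent within a group; outcome prevalence 50%; the AUROCs; and k = allogeneic SD / autologous SD, with the autologous SD set to 1.

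**Formulas.** Let D be the mean difference between outcome classes divided by the within-group SD.
- AUROC = Φ(D/√2), so D = √2 × Φ⁻¹(AUROC).
- log OR per unit = D/SD.

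AUROC depends on D alone, while the per-unit OR depends on D and the SD.

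**Equal discrimination, unequal spread.** At AUROC 0.80, D = 1.414 × 0.842 = 1.190. The autologous per-unit OR is exp(1.190) = 3.29 and the allogeneic one is exp(1.190/k). The rejection rates are from 2,000 to 3,000 simulated trials per scenario, and ranges span repeat runs. The IOR test is a Wald test of the interaction; the AUROC test is DeLong for independent samples.

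| k | Allogeneic OR | True IOR | IOR significant | AUROC difference significant |
|---|---|---|---|---|
| 1 | 3.29 | 1.00 | about 4% | 4-5% |
| 1.25 | 2.59 | 0.79 | about 8% | about 5% |
| 1.5 | 2.21 | 0.67 | about 17% | about 5% |
| 2 | 1.81 | 0.55 | 37-39% | 4-6% |

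Sensitivity at k = 2:
- AUROC 0.70 or 0.90 in both groups: 22% or 50%.
- Prevalence 30%, AUROC 0.80: 35%.
- 40 per group, AUROC 0.80: about 18%.
- 40 allogeneic and 75 autologous, AUROC 0.80: about 31%.

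**Unequal discrimination, equal per-unit OR.** AUROC 0.65 gives D = 1.414 × 0.385 = 0.545, and AUROC 0.80 gives D = 1.190. The per-unit ORs are equal when k = 1.190/0.545 = 2.18; both are then exp(0.545) = 1.72 and the IOR is 1. With 75 per group the IOR is significant in about 5% of trials and the AUROC comparison in about 46%.

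**Binary signs.** Identical sensitivity and specificity in both groups give IOR = 1, so the spread argument does not arise. The OR still does not fix accuracy: 0.75/0.75 gives (0.75/0.25) × (0.75/0.25) = 9, and 0.90/0.50 gives (0.90/0.10) × (0.50/0.50) = 9.

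**The case against.** The best defence is that the plan says what it means. It sets out to examine combined effects of measurement and transplant group and reads the interaction explicitly in OR terms. That is effect modification on the odds scale, for which the IOR is the standard test; the plan nowhere names equal AUROC as its null. This stands, and it limits the point to the step from the IOR to a statement about distinguishing.

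A reader might infer from the table that the planned test has an inflated type I error. It does not. In the rows with k above 1 the true IOR is not 1, and the test is detecting a real difference in per-unit OR. At k = 1 it holds its level.

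A reader might also infer that AUROC is the only correct scale and should replace the interaction model. The documents do not settle that. Variables and Procedures gives normal wall thickness in absolute terms (below 3 mm), so behaviour at a common cut-off can matter. In the example with AUROC 0.80 and k = 2, the autologous midpoint (D/2 = 0.595) gives sensitivity and specificity of Φ(0.595) = 72% each in autologous patients. In allogeneic patients the same cut-off gives Φ(1.190 − 0.298) = 81% and Φ(0.298) = 62%. Equal AUROCs conceal that, which is a reason to keep the model.

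The case for unequal spread is also modest. The endpoint uses baseline scans, taken at symptom onset in both groups on one platform, and restricting to non-aGvHD patients removes one source of allogeneic heterogeneity. That restriction also leaves fewer than 75 allogeneic patients if any have aGvHD.

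Finally, the outcome of the interaction model is not defined (which complication against which comparator). Neither an IOR nor an AUROC by group can be computed until it is.

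**Conclusion.** The point holds in a limited form and is minor. The planned IOR validly tests whether the per-unit OR differs between transplant groups. It does not by itself show whether measurements "measurements at baseline differ in distinguishing complications different from aGvHD", and no other planned analysis does. For continuous measurements the gap matters only if spread differs: negligible at equal SDs, small at a ratio of 1.25, substantial at 2. Those ratios, the AUROCs, the prevalence and normality are all assumptions, so the size in this trial is unknown and may be negligible. False signals from spread do not extend to binary signs with equal sensitivity and specificity. The primary accuracy endpoint is untouched, and this is a secondary question in a study that describes itself as a pilot.

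**What to change.** In Statistical Analysis, keep the interaction model and make four changes.

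1. For each continuous or ordinal measurement, report the AUROC for the complication outcome in each transplant group and the difference, with a DeLong (independent samples) or bootstrap 95% CI.
2. For each binary sign, report group-specific sensitivity and specificity with CIs.
3. Base the answer to secondary endpoint 2 on these estimates, and describe the IOR only as a between-group difference in per-unit OR.
4. Define the complication outcome so that it varies in both groups, for example infectious versus non-infectious among non-aGvHD patients.

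The cost is SAP wording and a few lines of R on data already collected, with no extra patients or procedures. The downsides are more estimates to report, an AUROC comparison not adjusted for covariates, and wide intervals. Power is about 46% for AUROC 0.65 versus 0.80 with 75 per group, and lower once aGvHD cases are excluded, so estimates with intervals should carry the message rather than p-values.

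### At least 16 ultrasound measurements are tested at P<0.05 in the secondary analyses, with a 'suggestive' band to 0.10 and no multiplicity control or exploratory label

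*Combined protocol and SAP*

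**What the plan says.** All references are to the combined protocol and SAP.

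- **Measurements.** Variables and Procedures introduces two lists, "The following ultrasound parameters will be collected" (7 items) and "The following CEUS parameters will be collected" (8 time-intensity quantities). It then states that "each single evaluation will be completed with the use of SWE", without saying how many stiffness values this yields.
- **Analyses.** Statistical Analysis plans allogeneic versus autologous group comparisons, univariable and multivariable logistic models for acute graft-versus-host disease (aGvHD), and interaction models by transplant group. Of the last it says that "for each US measurement, one interaction logistic regression model will be fitted".
- **Decision rule.** The same section reads "Statistical significance will be set at P value" < 0.05, followed by "P values between 0.05 and 0.10 will be further reported as suggestive".
- **Status.** Sample Size calculation calls the study a pilot, as the reason for having no formal calculation. Secondary endpoints names the associations with aGvHD and the allogeneic/autologous differences as endpoints. Primary endpoint concerns sensitivity, specificity and predictive values.

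The available Endpoints and SAP text does not adjust P values for the number of measurements, rank the measurements, name a key one, or call these P values exploratory.

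**The concern.** Many measurements are examined separately, each against the same unadjusted threshold, and a second label is given to results that miss it. With this many tests, some will cross one line or the other by chance. The report would present those in the same terms as real associations, and a reader could not tell them apart.

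What is at stake is the reading of individual measurements in the secondary endpoints. These are stated endpoints, so a 'significant' or 'suggestive' label on one measurement is likely to be taken as a result of the study.

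**Working it through.** The plan states no family-wise error rate, so there is no figure of its own to reproduce. The check counts the measurements and applies the plan's two thresholds.

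**1. Count (Variables and Procedures).**
- Conventional, 7: wall thickness, stratification, colour Doppler flow, strictures, free fluid, mesenteric nodes, mesenteric hypertrophy.
- Contrast-enhanced, 8: B, K, C, TTP, Area, ATM, PI, I.
- Shear wave elastography: at least 1.
- Total: 7 + 8 + 1 = 16 or more.

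**2. One family of 16 independent tests, no true effects.** The chance of at least one result below α is 1 − (1 − α)^16.
- α = 0.05: 1 − 0.95^16 = 0.560. Expected number: 16 × 0.05 = 0.8.
- α = 0.10 (significant or suggestive): 1 − 0.90^16 = 0.815. Expected number: 16 × 0.10 = 1.6.

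Under independence the chance passes 50% at 14 tests for P<0.05 and at 7 tests for P<0.10.

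**3. Correlated tests.** The documents give no correlations, so these values are assumptions. The figures come from simulating 16 equally correlated two-sided z-tests (200,000 draws); the zero row is exact.

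| Pairwise correlation | At least one P<0.05 | At least one P<0.10 |
|---|---|---|
| 0 | 56.0% | 81.5% |
| 0.2 | 51.6% | 77.4% |
| 0.3 | 47.5% | 73.0% |
| 0.5 | 37.4% | 60.7% |
| 0.6 | 31.9% | 52.7% |
| 0.7 | 26.3% | 44.5% |
| 0.9 | 14.6% | 25.9% |

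If only the 8 contrast-enhanced quantities are correlated with each other, the figures are 50.2% and 75.6% at 0.5, and 41.7% and 66.3% at 0.9.

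**4. Some measurements real.** If only 8 of the 16 had no true effect, independence gives 1 − 0.95^8 = 33.7% and 1 − 0.90^8 = 57.0% for at least one chance result among those 8.

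**5. Across analyses.** Take one test per measurement in each of the three analyses, using only the interaction odds ratio from each interaction model: 16 + 16 + 16 = 48 tests. Expected results with no true effects: 48 × 0.05 = 2.4 significant and 48 × 0.10 = 4.8 significant or suggestive. These expected counts do not depend on correlation, but they do assume that each test holds its nominal level.

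**6. Size of an adjustment.** For scale, Bonferroni over 16 measurements uses 0.05/16 = 0.003125 per test, and 1 − (1 − 0.003125)^16 = 4.9% within one family.

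**The case against.** The best defence is that this is a pilot, its primary endpoint is estimation, and a lenient screen can be a deliberate choice so that useful measurements are not missed. Much of that is fair. The primary endpoint is untouched, and unadjusted P values in a pilot are acceptable if the plan says they are exploratory. This plan does not say so. It uses pilot status only to waive the sample size calculation, then declares statistical significance and adds a looser label.

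A reader might also infer more than the documents support:

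- **That a chance finding is more likely than not, without conditions.** This needs no true effects. The Introduction cites 92.9% sensitivity and 94.4% specificity for contrast-enhanced ultrasound, so some measurements may well be informative. For P<0.05 in one family, it also needs correlation below about 0.3, and eight of the quantities come from a single time-intensity curve. With the suggestive band included, it holds up to a correlation of about 0.6.
- **That there are 80 tests.** Counting all three interpreted coefficients of each interaction model gives 16 + 16 + 48 = 80. But one of the three is the transplant-group effect at a measurement value of zero, which does not test a measurement. Removing it gives 64, and keeping only the interaction odds ratio gives 48. Even 48 assumes that every measurement enters the group comparisons and the univariable models; Statistical Analysis supports that reading but states one model per measurement only for the interactions.
- **That the false-positive rate for significance is doubled.** Significance stays at 0.05. The band doubles the chance that a null result receives some positive label.
- **That the pilot will carry the wrong measurements forward.** No passage says its purpose is to select measurements for a later study.

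Sparse findings such as strictures may also give conservative or inestimable tests, which lowers the effective count. In the other direction, the first secondary endpoint refers to weekly measurements, so the count could rise; the plan does not say by how much.

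**Conclusion.** The concern holds for the secondary association analyses. The plan's reporting rule makes chance positives likely there, and nothing in the plan limits or flags them.

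With no true effects, one family of 16 tests gives at least one P<0.05 with probability 56% (independent) or about 37% (assumed correlation 0.5). The probability of at least one significant or suggestive result is 81% or about 61%. On the 48-test reading, about 2.4 and 4.8 such results are expected. All of these figures fall if some measurements have real effects, and the probabilities also fall with stronger correlation.

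This should be changed before analysis. It does not threaten the primary endpoint.

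**What to change.** In Statistical Analysis, delete the sentence on suggestive P values and add wording along these lines:

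> P values for the secondary endpoints are exploratory. Within each secondary endpoint, odds ratios with 95% confidence intervals and unadjusted P values are reported alongside Benjamini-Hochberg adjusted P values across ultrasound measurements (false discovery rate 5%), with one test per measurement: the univariable odds ratio for the first endpoint and the interaction odds ratio for the second. A measurement is called significant only on its adjusted P value.

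To keep one test per measurement, the plan must also say which of the weekly examinations supplies the value for the first endpoint. The allogeneic versus autologous comparisons are not clearly tied to either endpoint, so the exploratory statement should cover them by name.

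With no true effects and independent or positively dependent tests, this limits the chance of any false claim to about 5% within each endpoint. It costs SAP wording and one line of R code, needs no further patients or data, and hides no estimate. The downside is that fewer secondary results are labelled positive. The loss of power with 75 allogeneic patients has not been calculated.
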